**PROTOCOL ABSTRACT**

The purpose of this study is to treat the language impairment of subjects with Primary Progressive Aphasia using transcranial direct current stimulation (tDCS) and high definition transcranial direct current stimulation (HD-tDCS). PPA is a slowly progressive impairment in language that may be observed in patients with neurodegenerative conditions such as Fronto-temporal dementia or, less commonly, Alzheimer's Disease. tDCS is a form of non-invasive brain stimulation in which very small current (here, 1.5 mA) is applied to the scalp. tDCS will be administered in ten 20 minute sessions over the course of two weeks. Language function will be assessed before, after 1 week of treatment, after 2 weeks of treatment and at 6 and 12 weeks after completion of tDCS. In a sub-study under this protocol, we will pair HD-tDCS with Constraint-Induced Language Therapy (CILT), which preliminary evidence has shown may be a useful speech therapy for individuals with PPA. In this sub-study, we will investigate whether HD-tDCS can enhance the potential benefits of speech therapy (usually very modest in PPA).

## OBJECTIVES

### **1.1 Overall Objectives of tDCS-Only Study**

The major objective of the project is to improve language function in patients with Primary Progressive Aphasia using tDCS.

### **1.2 HD-tDCS+CILT Sub-study Objectives**

The objective of the HD-tDCS+CILT sub-study is to improve language function in patients with Primary Progressive Aphasia using a combination of HD-tDCS and a form of intensive speech therapy called Constraint-Induced Language Therapy. The HD-tDCS+CILT sub-study shares many of the design features of the tDCS-Only study in 1.1, therefore, we will include additional information about HD-tDCS+CILT in its own section where relevant to help delineate the differences between these two studies. Any sections that do not include a HD-tDCS+CILT sub-section apply identically to both studies.

### **1.3 tDCS for svPPA Sub-study Objectives**

The objective of the tDCS with svPPA sub-study is to improve language function in patients with semantic variant Primary Progressive Aphasia using a combination of tDCS and speech therapy.

## **2. Primary Outcome Variable(s)**

Outcomes will be assessed with a variety of measures of language including naming and picture description. We will contrast performance before and after tDCS using customary statistical techniques (e.g., ANOVA, t-test, etc). We will also perform analyses of MRI data from participants to determine if there is a correlation between measures such as blood flow and atrophy and improvement from tDCS.

## **BACKGROUND**

In approximately 2000, Nitsche & Paulus demonstrated that weak direct currents applied to the skull could influence brain function. Although still at a relatively early stage of development, the technique has been demonstrated to influence cognition and behavior in more than 300 studies. Importantly, as demonstrated by work in our lab (Kessler, Turkeltaub, Benson, & [name], 2012), as well as other sites around the world, the technique has proven to be quite safe. To date, no major adverse effects have been reported with tDCS. We recently reported that 4 weeks of daily tDCS delivered to young normal subjects was well-tolerated with no adverse effects observed (Richmond, [name],

[name], Vyas, & Olson, 2013). tDCS has been used in the treatment of patients with neurodegenerative diseases (e.g., Benninger et al., 2010; Boggio et al., 2012; Hansen, 2012). We are aware of only one report in which tDCS was administered to a subject with PPA; there was significant improvement in some language functions in the absence of adverse effects (Wang, Wu, Chen, Yuan, & Zhang, 2013). HD-tDCS is an emerging technique of noninvasive brain stimulation that has been tested in a limited number of aphasic populations with comparable effects to traditional tDCS (Sebastian, Tsapkini & Tippett, 2016; Richardson et al., 2015). This new type of stimulation will provide a more focal flow of current than traditional tDCS. Primary progressive aphasia (PPA) is a behavioral disturbance characterized by the insidious onset and slow progression of language impairments in the context of a neurodegenerative disease. In different patients, the deficits may differentially impact comprehension, semantics or verbal fluency. Autopsy studies demonstrate that most patients with PPA suffer from Fronto-temporal dementia but Alzheimer's Disease, Dementia with Lewy Bodies and cortico-basal ganglionic degeneration may also cause the disorder. The disorder leads to a profound impairment in language and, ultimately, to a generalized severe dementia involving all domains of cognition. CILT is an intensive language therapy protocol, first developed by Pulvermuller and colleagues (2001) for use in language rehabilitation following stroke. The central principles of CILT are massed practice over many hours, combined with restricting communication to use of verbal language only (i.e., no gestures or other communication). Throughout the course of a CILT treatment, the difficulty of each stage of therapy is also scaled to individual patient performance, such that patients' language abilities can be sequentially behaviorally "shaped" to ensure a low rate of failure and a gradual increase of difficulty as improvements are made and new skills are retained. Traditional speech therapies are not typically as beneficial for individuals with PPA relative to individuals with post-stroke aphasia due to the progressive nature of the disorder. However, because the central principles of CILT involve massed practice over many hours, paired with constraining communication to the use of language, CILT may thus be useful in the *retention* of language in PPA in addition to aiding in the reacquisition of language after stroke. A recent study has shown modest benefits of an intensive CILT protocol in two individuals with PPA (Hameister et al., 2016), but further questions remain regarding how effective CILT may be for PPA and how long patients can expect the benefits of CILT to last.

## CHARACTERISTICS OF THE STUDY POPULATION

### **1. Target Population**

Adult subjects between the ages of 45 and 80 with a diagnosis of Primary Progressive Aphasia.

PPA is caused by a neurodegenerative disease. Because these disorders are exceedingly rare under the age of 45 we will not include subjects less than 45 years of age because of uncertainty regarding the diagnosis. As PPA is a rare disorder and we hope to maximize our sample size, all subjects with this diagnosis will be invited to participate.

### **1.1 Target Population for svPPA sub-study**

Adult subjects between the ages of 45 and 80 with a diagnosis of semantic variant Primary Progressive Aphasia.

## **2. Accrual**

There is no information on the basis of which to determine the appropriate sample size. All subjects with Primary Progressive Aphasia who meet Inclusion and Exclusion criteria will be invited to participate.

## **3. Key Inclusion Criteria for tDCS-Only Study**

Study subjects must meet all of the following inclusion criteria: 1. Presence of aphasia attributable to Primary Progressive Aphasia, 2. Between the ages of 45 and 80, 3. Must be able to understand the nature of the study, and give informed consent.

### **3.1 Key Inclusion Criteria for HD-tDCS+CILT sub-study**

Study subjects must meet all of the following inclusion criteria: 1. Presence of aphasia attributable to Primary Progressive Aphasia, 2. Between the ages of 45 and 80, 3. Must be able to understand the nature of the study, and give informed consent. 4. Picture-naming performance at study screening must be at least 50% accurate in the easiest category of screening images (High Frequency Objects)

### **3.2 Key Inclusion Criteria for tDCS for svPPA**

Study subjects must meet all of the following inclusion criteria: 1. Presence of aphasia attributable to the semantic variant of Primary Progressive Aphasia. 2. Between the ages of 45 and 80. 3. Must be able to understand the nature of the study, and give informed consent.

## **4.1 Key Exclusion Criteria for tDCS-Only and HD-tDCS+CILT**

1. Cognitive impairment of sufficient severity to preclude giving informed consent (MMSE < 15).
2. History of seizures or unexplained loss of consciousness; tDCS and HD-tDCS are not associated with seizures but as little information is available we exclude subjects with seizures or unexplained loss of consciousness

3. Pregnancy. There is no evidence of adverse effects from tDCS or HD-tDCS on the fetus but as the question has not been well-studied, we exclude subjects who are pregnant. All women of child-bearing age (that is, still menstruating) will be required to have a negative urine pregnancy test prior to receiving tDCS or HD-tDCS.
4. Subjects with metallic objects in the face or head other than dental apparatus such as braces, fillings, and implants.
5. Subjects with Pacemakers or ICDs.
6. Subjects with previous craniotomy or any breach in the skull; skull defect could be associated with shunting of current leading to unpredictable location and level of current affecting the brain.
7. Subjects with a history of stroke
8. Subjects with a history of small vessel disease

#### ***4.2 Key Exclusion Criteria for tDCS with svPPA***

Exclusionary criteria for the tDCS with svPPA sub-study include all the criteria listed above, but also include:

1. Usage of sedating medications

#### ***5. Vulnerable Populations***

Pregnant women, fetuses, neonates or prisoners are not included in this research study; children 18 and older can participate.

#### ***6. Populations vulnerable to undue influence or coercion***

Special Considerations for Aphasic Patients: Because this protocol involves the enrollment of subjects who are known to have language deficits, some subjects will have difficulty understanding what has been explained to them about the protocol, either verbally or in writing. In other cases, subjects with relatively mild deficits or deficits restricted to the domain of language production will be able to understand what has been explained to them quite readily. For subjects about whom there is uncertainty regarding the comprehension of the ICF and nature of the proposed investigation, we will require that informed consent be obtained from both the patient and a legally authorized representative. The Informed Consent Form (ICF) will be provided to the subject (and to their legally authorized representative when needed) and will be reviewed in detail by the PI or another designated member of the research team. After reading and verbally reviewing the document, the subject (and their representative, as needed) will be asked if there are any questions

or concerns. If the subject (and their representative, as needed) indicates agreement with the participation by signing the ICF, indicate that there are no additional questions, and meet inclusion/exclusion criteria, the subject will be included in the study. In the event that subjects have intact language comprehension and do not require a legally authorized representative, we will document on the consent form that a co-signature by such an individual is not needed by writing "Not applicable" or "N/A" on the signature line of the legally authorized representative. Students will not be enrolled as the disease occurs relatively late in life (50s would be the earliest). The condition is not consistent with employment so subjects will not be Penn employees. The compensation is very modest (\$25/hour); we believe that it is very unlikely that this modest compensation alone would be sufficient to induce a potential subject to participate.

## ***7. Subject Recruitment***

Patients with Primary Progressive Aphasia will be recruited from two sources: 1) the clinical practices of Drs. [name], [name], and [name] at the Hospital of the University of Pennsylvania, 2) patients participating in [name] project entitled "Neural Basis for Frontotemporal Degeneration" (IRB #298201). Potential patients identified in the clinical practices of the investigators will be contacted directly by the relevant physician. Patients recruited from [name] on-going research project will be contacted by the trained research staff with whom they are currently interacting. We also will use the attached flyers to recruit patients around the University of Pennsylvania campus and Hospital of the University of Pennsylvania grounds, as well as on online FTD/PPA support groups and in-person support groups around the Philadelphia area. Finally, we will sometimes send an email script with information about the study to participants who express an interest in learning more about the research study. Because this is a study of aphasia, a language disorder, oftentimes it is easier for participants to understand information if it is written down and they have time in advance to look things over. This email script will in no way replace the consent form or the consenting process, but we have found these scripts helpful in other studies.

## ***8. Real time safety monitoring***

Subjects and equipment will be monitored at all times during tDCS and HD-tDCS studies by a trained member of the research personnel list approved to be on the protocol. During the first stimulation session, participants will come to the lab here at the University of Pennsylvania and a physician will be on call within 5 minutes of the testing room. As long as the subject does not experience any adverse events during that first stimulation session and the research staff have no

reservations, then in all subsequent stimulation sessions, whether conducted in the patient's home or in the laboratory here at the University of Pennsylvania, one of the physicians associated with the study will respond to any concerns within 24 hours. Additionally, the trained personnel administering stimulation will look for any evidence of discomfort in the participant and will verbally inquire about any discomfort. The investigator or trained personnel will also observe and monitor the equipment. In the unlikely event that either the subject or the person administering tDCS or HD-tDCS has significant concerns and the PI cannot be immediately contacted, the subject would be escorted to the Emergency Room.

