#### ***2.1 Design of tDCS-Only Study***

This is a sham-controlled, full cross-over study design. All subjects with PPA will participate in ten 20-minute tDCS stimulation sessions over the course of 2 weeks using 1.5 mA current. A battery of language tasks will be administered before stimulation sessions, after the 10 sessions, and again at 6 and 12 weeks after the stimulation sessions. The 12-week follow up session will serve as the "baseline" session for the following stimulation sessions. All subjects will also participate in ten 20-minute sham stimulation sessions over the course of 2 weeks. During sham tDCS, a 1.5 mA current will be delivered for approximately 30 seconds at the beginning of the sham session before being extinguished over the course of seconds. Participants will be randomly assigned to receive sham or tDCS stimulation first.

For example, a subject who is assigned to sham stimulation sessions first will first undergo baseline language testing. Then the subject will participate in ten 20-minute sham stimulation sessions over the course of 2 weeks. The subject will go through follow up language testing after the 10th sham stimulation sessions as well as 6 and 12 weeks following the sham stimulation sessions. The 12 week follow up session will serve as the "baseline" for the tDCS stimulation sessions, after which the subject will participate in ten 20-minute tDCS stimulation sessions over the course of 2 weeks, using 1.5 mA current.

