## **RESOURCES NECESSARY FOR HUMAN RESEARCH PROTECTION**

Research staff related to this project include the PI, Co-investigators (Drs. [name] and [name]) and other personnel. All research staff will undergo training on research practices involving human subjects, including the protection of subject confidentiality, and will maintain current certification in patient oriented research. Moreover, all investigators will have experience administering tDCS.

During the first stimulation session, participants will come to the lab here at the University of Pennsylvania and a physician will be on call within 5 minutes of the testing room. As long as the subject does not experience any adverse events during that first stimulation session and the research staff have no reservations, then in all subsequent stimulation sessions, whether conducted in the patient's home or in the laboratory here at the University of Pennsylvania, one of the physicians associated with the study will respond to any concerns within 24 hours. The trained personnel administering stimulation will look for any evidence of discomfort in the participant and will verbally inquire about any discomfort. The investigator or trained personnel will also observe and monitor the equipment. In the unlikely event that either the subject or the person administering tDCS has significant concerns and the PI cannot be immediately contacted, the subject would be escorted to the Emergency Room.

Staff will also be trained on the correct administration of the specific psychometric tests of language and cognition employed in proposed research. Subject Recruitment: Patients with PPA will be recruited from two sources: 1) the clinical practices of Drs. [name], [name], and [name], 2) [name] IRB-approved protocol entitled "Neural Basis for Frontotemporal Degeneration" (#298201). Potential subjects identified in the clinical practices of Drs. [name], [name] and [name] will be contacted by their treating physician. Potential subjects involved in research with [name] and his team will be contacted by the research staff with whom they interact in the on-going research project.

Facilities: Subjects will be stimulated and tested in HUP or Perelman School of Medicine buildings. Depending on the availability of rooms, three testing sites may be employed: Neurology out-patient

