offices in the Perelman Center, Neurology out-patient offices on Ravdin 2 or the laboratory of [name] (Gibson 3). The HD-tDCS apparatus is portable and no special equipment is required. Additionally, if it is convenient for the patient, we may conduct stimulation sessions in the patient's home. In order to be eligible for home visits, patients must live within 40 miles, or approximately one hours, of the University of Pennsylvania. Ultimately, the discretion for eligibility and scheduling will be up to the researcher and the Principal Investigator, in order to best effectively and efficiently manage the lab's resources. If patients do qualify for home visits, they will come to the lab for their first stimulation session. If the patient does not experience any adverse events during that stimulation session and if the other requirements are met, then all subsequent stimulation sessions would be conducted in the patient's home. Again, we would like to stress that this is only an option, not a requirement, which patients may choose if it is more convenient for them. Patient visits not requiring the use of tDCS may be conducted at the patient's home if this situation proves to be more convenient for the patient.

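### The nearby-physician safeguard covers only the first stimulation session, which is sham for half of participants, so their first full-length active session needs no physician nearby

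*Combined protocol and SAP*

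**What the plan says.** Section 8 (Real time safety monitoring) brings each participant to the lab for the first stimulation session, when "a physician will be on call within 5 minutes of the testing room". The condition for relaxing this reads: "As long as the subject does not experience any adverse events during that first stimulation session". Staff must also have no reservations. For every later session, in the lab or at home, the requirement is that "one of the physicians associated with the study will respond to any concerns within 24 hours". The section on resources for human research protection repeats the rule, with the same scope: "the research staff have no reservations, then in all subsequent stimulation sessions". Its Facilities paragraph adds: "If patients do qualify for home visits, they will come to the lab for their first stimulation session". Sessions after that one may take place at home. Home visits are optional, are at the discretion of the researcher and the PI, and carry a distance limit: "patients must live within 40 miles, or approximately one hours, of the University of Pennsylvania".

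Study Design 2.1 treats sham visits as stimulation sessions: "All subjects will also participate in ten 20-minute sham stimulation sessions over the course of 2 weeks". Study Procedures 1.1, 1.2 and 1.3 each give half of subjects ten sham sessions first, followed by ten real ones.

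Other protections run through both blocks. Trained personnel monitor every session, symptoms are queried before each stimulation, the screening form is repeated when each block begins, and there are rules for stopping if language worsens. If there are significant concerns and the PI cannot be reached at once, "the subject would be escorted to the Emergency Room".

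**The concern.** The rule has a clear logic: place a physician close by at first exposure, then relax once the participant has tolerated it. That works only if the first session is a real exposure. For the sham-first sequence it is a brief one. A sham visit can reveal early itching or burning under the electrode, but it cannot show how the participant tolerates 20 minutes of current. Those participants pass the test before any full-length stimulation and then start active treatment under the relaxed rule, possibly at home up to about an hour away.

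The two sequences are therefore protected differently at the same clinical milestone. Active-first participants have a physician nearby at their first full exposure; sham-first participants need not. At stake is physician proximity at that one session, not supervision in general. PPA-specific experience is thin: the Background section and Potential Study Risks cite one treated subject, and the latter describes the data as very limited. Monitoring also relies partly on asking participants about discomfort, in a population where some have difficulty with comprehension.

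**Working it through.** The plan gives no figure on this point to reproduce. The check sets the safety rule beside the cross-over order and sizes the gap.

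**Does the rule restart at cross-over?**
- Section 8 and the resources section speak of one first session and then of all subsequent ones. That wording does not support reading the rule as the first session of each block.
- Reading it as the first active session does not work either. Design 2.1 calls sham visits stimulation sessions, and a rule tied to active current would signal the allocation.
- Procedures 1.1, 1.2 and 1.3 repeat the screening form at the start of each block, but attach no physician cover to it.
- So the rule does not restart. For sham-first participants, the first active session is session 11 of 20.

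**How many participants?**
- Study Duration 3.1 and 3.2 each expect about 10 subjects a year for about 2 years: 10 × 2 = 20 per study.
- Half start with sham: 20 × 0.5 = 10 in the tDCS-only study and 10 in HD-tDCS+CILT.
- No enrolment figure is given for the svPPA sub-study.
- The number whose first active session would be at home is unknown: 0 to about 10 per study.

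**How much current does the covered sham session deliver?**
- Active session: 20 min × 60 = 1200 s.
- Sham at full intensity: about 30 s in Design 2.1, the svPPA design section and Potential Study Risks; about 10 s in Procedures 1.1 and 1.3.
- 10 / 1200 = 0.8% and 30 / 1200 = 2.5%. These exclude ramps; Procedures 1.2 adds a 30-second ramp-up and ramp-down in the HD sub-study.
- In svPPA, the design section says 20 minutes. Procedures 1.3 starts therapy after 10 minutes and then describes 20 minutes of overlap, which implies 10 + 20 = 30 min = 1800 s. On that reading the range is 10 / 1800 = 0.6% to 30 / 1800 = 1.7%.
- These are ratios of duration. They do not measure how much a sham session reveals about tolerance.

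**How long until the first active session?**
- 2 weeks of sham + 12 weeks to the follow-up that serves as second baseline = 14 weeks after the first sham session.
- With the ±1 week visit window in Procedures 1.1 and 1.2, 13 to 15 weeks.

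**What would covering both blocks change?**
- Covered sessions per participant rise from 1 of 20 to 2 of 20.
- The share of participants whose first full-length active session is covered rises from about 50% to 100%.

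**The case against.** The strongest reply is that the risk is too low for this to matter. Potential Study Risks reports no significant adverse effects in more than 500 sessions, says risk is the same at home as in the lab, and notes that the IRB regards tDCS as minimal risk in normal subjects and has deemed HD-tDCS minimal risk. Elsewhere the protocol cites four weeks of daily stimulation tolerated by young normal subjects, more than 200 sessions on this apparatus, and use in degenerative brain disease without adverse effects. It describes no late-onset or duration-dependent harm. The common effect it names, itching or mild burning, can appear during sham because sham includes real current. Nor is the 24-hour response the route for serious problems: staff would try the PI and then go to the Emergency Room. Many sessions will be in hospital or medical school buildings anyway.

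Most of this stands, and it keeps the point minor. It does not answer the point itself. The protocol still judged a nearby physician worth providing at first exposure, and neither low risk nor equal risk at home explains why only one sequence should have that cover when full-length stimulation begins.

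A drafting objection also has merit: a rule covering every block would take in the optional HD-tDCS booster, which does not need it. The extra lab visit would also fall on home-treated patients in both sequences. The wording below deals with the booster. The visit is a real but small burden.

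**Conclusion.** The concern holds as a minor safety gap that is cheap to close. As written, about half of participants in each study can begin full-length active stimulation with no physician required nearby, having met the condition for relaxed cover on a session with about 10 to 30 seconds of full-intensity current. That is about 10 people in the tDCS-only study and about 10 in HD-tDCS+CILT, assuming the approximate accrual is met and allocation is even; the svPPA number cannot be given. How many would be at home is unknown. The gap concerns physician proximity only, expected harm is small on the safety experience the protocol reports, and no efficacy result is affected.

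**What to change.** In section 8, the resources section and its Facilities paragraph, attach the lab visit and the on-call physician to the opening session of each of the two cross-over blocks, and make the step-down within a block depend on that block's own opening session. The protocol already uses the start of a block as the trigger for repeating the screening form. Naming the two cross-over blocks leaves out the HD-tDCS booster, which is reasonable because everyone who reaches it has already completed an active block.

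Apply the rule to both sequences. For active-first participants the second covered session is sham, so it adds little protection, but covering only the sham-first group would reveal allocation.

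The cost is a wording change in three places, one more on-call session per participant (1 × 20 = about 20 per study over 2 years), and at most one more lab visit for each participant using home visits. If the sponsor prefers to cover the booster too, that adds one session for each participant who opts in.
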